8.8.3.4. Time to Clinical Benefit and Time to Response

Time to clinical benefit (TCB) will be analyzed for subjects achieving CBR (MR or better) prior to initiation of new antineoplastic therapy as evaluated by investigators. Time to initial response as well as best response will be derived.

Time to initial clinical benefit response is defined as the interval between the date of first dose and the date of initial documentation of a response (MR or better). Time to best response is defined as the interval between the date of first dose and the date of initial documentation of the best response that a subject achieved prior to initiation of new antineoplastic therapy.

Similarly, time to response will be analyzed for subjects achieving PR or better prior to initiation of new antineoplastic therapy as evaluated by investigators.

For Cohorts 1 and 3 ibrutinib monotherapy, time to clinical benefit and time to response will be analyzed for subjects achieving response prior to initiation of dexamethasone or new antineoplastic therapy, whichever occurs first.

Time to clinical benefit and time to response will be summarized descriptively by treatment cohort as a continuous variable.

8.9. Safety Analyses

All safety analyses will be based on the safety population.

In Cohorts 1 and 3, subjects will be on ibrutinib monotherapy and may convert to ibrutinib and dexamethasone combination therapy at the discretion of the investigator after a confirmed PD on ibrutinib monotherapy. Thus the safety data (e.g. incidence of TEAEs, laboratory values) will be presented and distinguished as with and without dexamethasone for subjects in Cohorts 1 and 3, when applicable.

Table 7: Summary of Safety Analyses to be Performed

Category	Analysis	Summarize By	Listing
Adverse Events			
General	Overall summary	Study Period	
	TEAEs	SOC+ PT+Study Period; PT+ toxicity grade+Study Period	
	Grade 3 or worse TEAE	SOC+ PT+Study Period; PT+ toxicity grade+Study Period	
	Ibrutinib Related TEAE	SOC+ PT (Whole Study Period only)	
	Dexamethasone Related TEAE	SOC+ PT (Whole Study Period only)	
	Grade 3 or worse Ibrutinib Related TEAE	SOC+ PT (Whole Study Period only)	
	Grade 3 or worse Dexamethasone Related TEAE	SOC+ PT (Whole Study Period only)	
	TEAEs leading to treatment discontinuation		✓
	TEAEs leading to Ibrutinib discontinuation	SOC+ PT (Whole Study Period only)	
	TEAEs leading to Dexamethasone discontinuation	SOC+ PT (Whole Study Period only)	
	TEAEs leading to dose reduction or dose withheld		✓
	TEAEs leading to Ibrutinib dose reduction	SOC+ PT+Study Period	
	TEAEs leading to Dexamethasone dose reduction	SOC+ PT+Study Period	
	TEAEs leading to Ibrutinib dose withheld	SOC+ PT+Study Period	
	TEAEs leading to Dexamethasone dose withheld	SOC+ PT+Study Period	
	Serious TEAEs	SOC+ PT + Study Period; PT + toxicity grade + Study Period	✓
	Ibrutinib Related Serious TEAEs	SOC+ PT (Whole Study Period only)	
	Dexamethasone Related Serious TEAEs	SOC+ PT (Whole Study Period only)	
	Treatment emergent bleeding events	PT + toxicity grade+Study Period	

Category	Analysis	Summarize By	Listing
	Treatment emergent major hemorrhage	PT + toxicity grade+Study Period	✓
	Treatment emergent atrial fibrillation and atrial flutter events		✓
Death	Death within 30 days of last study treatment	Whole Study Period	
	All Deaths		✓
Laboratory Evaluations			
Hematology	Measured values and change from baseline	Visit+Study Period	
	Treatment emergent worst post-baseline low abnormalities	Toxicity grade+Study Period	
	Shift of toxicity grade in low direction	Toxicity grade+Study Period	
Chemistry	Measured values and change from baseline	Visit+Study Period	
	Treatment emergent worst post-baseline abnormalities	Toxicity grade+Study Period	
	Shift of toxicity grade in low direction	Toxicity grade+Study Period	
	Shift of toxicity grade in high direction	Toxicity grade+Study Period	
	Shift from baseline in Creatinine Clearance	Study Period	
	DILI related lab criteria	Study Period	
	Liver function abnormalities	DILI; NCI criteria; Hy's Law	✓, only if any potential Hy's Law identified
	Treatment emergent abnormal uric acid	Study Period	
Vital Signs			
General	Measured values and change from baseline	Visit+Study Period	
	Shift of ECOG Performance Status	Study Period	
Other Safety Observations			
General	Other malignancy	Treatment Emergent Period (primary analysis) + Study Period	✓

PT = preferred term; SOC = system organ class

Study Periods refer to Whole Study Period and Monotherapy Period

DILI = drug induced liver injury

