### **6.3.3 Combination of PCI-32765 and Dexamethasone Dosing**

#### **6.3.3.1 For Subjects with PD (Cohorts 1 and 3)**

At the discretion of the investigator and after Cycle 1, subjects in Cohorts 1 and 3 who have PD and who are clinically stable, without significant worsening of symptoms or hematologic status (ie, meet all entry criteria for the study in regard to symptoms and hematology), will be eligible to receive dexamethasone 40 mg orally once per week in addition to continued treatment with PCI-32765. PD should be confirmed or have repeat laboratory samples collected prior to addition of dexamethasone. Dexamethasone administration may commence at any time during a PCI-32765 cycle. Blood samples for PK should be obtained during the initial cycle with added dexamethasone (Cohort 1 and 3 only), according to [Section 7.1.2](#).

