4. STUDY POPULATIONS AND ANALYSIS SETS

The analysis and summary of data for this study will be performed using the following populations:

All enrolled population: All subjects who signed the informed consent form and were enrolled to one of the treatment cohorts. This population will be used to summarize disposition information.

All treated population: All enrolled subjects who received at least one dose of study drug. This population will be used to summarize subject enrollment, demographics, baseline and disease characteristics, prior therapies, and concomitant medications. This population is referred to as the “modified intent-to-treat (mITT) population” in the protocol. This is the primary analysis population for efficacy endpoints.

Response evaluable population: All enrolled subjects who received at least one dose of study drug and underwent at least one response assessment after start of treatment. Response rates (CBR rate and ORR) will be analyzed based on response evaluable population and will be considered as sensitivity analyses.

Safety population: All enrolled subjects who received at least one dose of study drug. This population will be used for analyzing the safety (including dosing) data.

Subjects in treated, response evaluable and safety populations will be analyzed according to the actual treatment received (i.e. as treated).

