8.2. Analysis of the Conduct of the Study

8.2.1. Subject Enrollment and Disposition

Subject enrollment will be summarized by country, study site and treatment cohort.

The disposition of all enrolled subjects will be summarized by treatment cohort:

- Number of subjects as enrolled, number of subjects as treated, number (%) of subjects in safety and response evaluable populations
- Number (%) of subjects who are still on study treatment.
- Number (%) of subjects with dexamethasone added (Cohorts 1 and 3 only).
- Number (%) of subjects who discontinued the study treatment and reason for discontinuation
- Number (%) of subjects who exited the study and reason for study exit
- Descriptive statistics for time on study; time on study is defined in the same way as overall survival with reversed censoring, i.e., subjects who died will be censored at death date. The Kaplan-Meier method will be used to estimate the median time on study.

The percentages will be based on the number of subjects treated.

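### In Cohorts 1 and 3, the SAP's denominator for dexamethasone-specific adverse events includes subjects who never receive dexamethasone, and no period or analysis set delivers the promised display with dexamethasone

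*SAP*

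**What the plan says.** SAP 8.9 opens with the rule "All safety analyses will be based on the safety population". SAP 4 defines that population: "All enrolled subjects who received at least one dose of study drug. This population will be used for analyzing the safety (including dosing) data". There is one such set, and it makes no reference to dexamethasone exposure.

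All subjects in Cohorts 1 and 3 start on ibrutinib alone. SAP 8.9 says that they "may convert to ibrutinib and dexamethasone combination therapy at the discretion of the investigator after a confirmed PD on ibrutinib monotherapy". Protocol 6.3.3.1 sets the conditions: "At the discretion of the investigator and after Cycle 1, subjects in Cohorts 1 and 3 who have PD and who are clinically stable", and without significant worsening of symptoms or hematologic status. Because of this, SAP 8.9 undertakes to separate the safety data in these cohorts by dexamethasone use, where applicable.

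SAP Table 7 contains six dexamethasone-specific rows:

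- Four are for the whole study period only: dexamethasone-related events, their Grade 3 or worse subset, their serious subset, and events leading to dexamethasone discontinuation.
- Two are shown by study period: events leading to dexamethasone dose reduction, and the row "TEAEs leading to Dexamethasone dose withheld".

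The table's footnote fixes the available periods: "Study Periods refer to Whole Study Period and Monotherapy Period". SAP 8.3 starts the whole study period at the first dose of study drug and ends the monotherapy period no later than the day before dexamethasone is added. SAP 5.7 defines a treatment-emergent period overall and one for monotherapy, but none that starts with dexamethasone.

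**The concern.** A subject who is never given dexamethasone cannot have an event attributed to it, or an event that leads to its being stopped, reduced or withheld. In Cohorts 1 and 3 such subjects still count in the denominator of those rows, so the percentages fall below the risk among subjects who took the drug.

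The period definitions leave a second gap. With only whole-study and monotherapy periods, the display with dexamethasone can only be the whole cohort over the whole study. That includes the time before dexamethasone and the subjects who never received it.

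Safety is a secondary endpoint (Protocol 4.2.2, SAP 2.2). In Cohorts 2 and 4 all subjects are planned to receive dexamethasone in the first cycle (Protocol 2.5), so the same rows there come close to per-recipient percentages. One row would therefore carry two meanings across the four cohorts.

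**Working it through.** The plan states no adverse event rate, and no number given dexamethasone, for Cohorts 1 and 3. There is no figure to reproduce, and the check is arithmetic on the denominator.

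**Inputs**

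- N, subjects treated: 13 in Cohort 1 and 18 in Cohort 3. These are Stage 1 enrollment figures from Protocol 2.4.5, used as a stand-in for the number treated.
- m, subjects given at least one dexamethasone dose: not in the documents; assumed.
- x, subjects with a given dexamethasone-specific event: not in the documents; assumed.

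**Formula**

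- Reported percentage under SAP 4 and 8.9: x/N.
- Percentage among recipients: x/m.
- Since x/N = (x/m) × (m/N), the reported figure is the per-recipient figure multiplied by m/N.

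**Illustrations (m and x assumed)**

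| Cohort | N | m | x | Reported x/N | Among recipients x/m | Factor m/N |
|---|---|---|---|---|---|---|
| 1 | 13 | 4 | 2 | 15.4% | 50.0% | 0.31 |
| 1 | 13 | 7 | 3 | 23.1% | 42.9% | 0.54 |
| 3 | 18 | 5 | 2 | 11.1% | 40.0% | 0.28 |
| 3 | 18 | 9 | 3 | 16.7% | 33.3% | 0.50 |
| 3 | 18 | 18 | 6 | 33.3% | 33.3% | 1.00 |

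**Range.** For m from 4 to 10 of 13, the factor runs from 4/13 = 0.31 to 10/13 = 0.77. For m from 5 to 14 of 18, it runs from 5/18 = 0.28 to 14/18 = 0.78.

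**When it would be negligible.** The relative understatement is 1 − m/N. It stays below 10% only if m is at least 12 of 13 (1 − 12/13 = 7.7%) or 17 of 18 (1 − 17/18 = 5.6%). At 11 of 13 it is 15.4%, and at 16 of 18 it is 11.1%.

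**Scope of the formula.** It applies only to the six dexamethasone-specific rows, where every event must come from a recipient. For all-cause events, the whole-study column mixes time before and after dexamethasone and mixes recipients with non-recipients. The documents do not determine the direction of any difference there.

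**The case against.** The strongest reply is that the denominator is inferred. SAP 8.9.1 promises only the number and percentage of subjects with events. The one explicit denominator sentence, using subjects treated, is in SAP 8.2.1 on disposition. SAP 4 says subjects are analyzed by the treatment actually received, and SAP 8.9 says safety in these cohorts will be separated by dexamethasone use where applicable. A programmer could take these as room for a recipients-only denominator. That is fair, but the room is not a rule. The only stated population for safety is the full safety population, four of the six rows are expressly whole-study, and no recipient subset exists to which the separation could attach.

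Other points stand and limit the concern:

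- Counts are not diluted. SAP 8.2.1 reports how many subjects in Cohorts 1 and 3 had dexamethasone added, so x/m can be approximated by hand.
- The whole-cohort percentage is a valid answer to a different question: how often such an event occurs under a strategy of ibrutinib with optional dexamethasone after progression.
- The protocol requires the split by dexamethasone only for efficacy endpoints (Protocol 8.1). The safety split is the SAP's own undertaking.

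A reader might infer that a lower rate in Cohorts 1 and 3 than in Cohorts 2 and 4 would be due solely to the denominator. The documents do not support that. Recipients in Cohorts 1 and 3 are clinically stable subjects chosen by the investigator after progression and after Cycle 1. In Cohorts 2 and 4 dexamethasone starts on Day 4 of Cycle 1, or Day 8 in the Cohort 4 expansion (Protocol 6.3.3.2 and 6.3.3.3). Rates could differ even with matched denominators, and SAP 8.8 plans no inferential comparison among cohorts.

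A reader might also infer that the monotherapy cells of the reduction and withheld rows must be zero. If events are assigned by onset date, one that begins before dexamethasone and later leads to its being reduced or withheld could fall there. The SAP does not say which date governs.

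**Conclusion.** The concern holds in a limited form. Applied as written, SAP 4, 8.9 and Table 7 give percentages for dexamethasone-specific events in Cohorts 1 and 3 that are scaled down by the fraction of the cohort given dexamethasone. The undertaking to show safety with dexamethasone has no period or analysis set behind it.

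The direction for the dexamethasone-specific rows is certain unless every subject in the cohort receives dexamethasone. The size is not known: the factors above rest on assumed exposure counts and on enrollment standing in for the number treated. The matter is descriptive and confined to two cohorts. It affects neither the primary endpoint nor the stage decisions. It is still worth correcting, because it follows from a stated rule and the correction needs no new data.

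**What to change.** In SAP 4, 5.7, 8.3 and Table 7, for Cohorts 1 and 3:

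1. Define a dexamethasone-treated subset: subjects with at least one dose of dexamethasone.
2. Define a combination period from the first dexamethasone dose through 30 days after the last study drug or the day before subsequent anti-myeloma therapy, whichever comes first.
3. Use the subset as the denominator for the combination-period display and for the dexamethasone-related, discontinuation, reduction and withheld rows. Whole-cohort percentages may be shown alongside.
4. In the reduction and withheld rows, either remove the monotherapy period or state how events that began before dexamethasone are assigned.

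The cost is SAP wording and one extra table column. The dexamethasone start date is already needed for time to addition of dexamethasone (SAP 8.6) and for monotherapy censoring (SAP Tables 4 and 5). The drawback is a small denominator, so percentages should be shown with their counts.

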#### **3.2 Secondary Objectives**

Secondary objectives are to evaluate the efficacy of PCI-32765 in this population as assessed by the following:

- Duration of clinical benefit (DCB)
- Objective response rate (ORR)
- Duration of objective response (DOR)
- Safety (assessed by reporting of SAEs, AEs, and treatment-related discontinuations)
- Pharmacokinetics (assessed by sampling and testing for drug and metabolite levels at designated time points)

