### **8.3.5 Safety Endpoint**

Safety summaries will include tabulations in the form of tables and listings. The frequency (number and percentage) of treatment-emergent AEs will be reported by MedDRA® System Organ Class and Preferred Term. Additional AE summaries will include AE frequency by AE severity and by relationship to study drug.

Adverse events requiring permanent discontinuation of study drug will be summarized separately, both overall and by AE severity and by relationship to study drug.

The incidence of clinically significant abnormal laboratory values and vital signs will be summarized.

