### 9.2.4 Causality

The investigator is to assess the causal relation (ie, whether there is a reasonable possibility that the study drug caused the event) using the following definitions:

Unrelated: Another cause of the AE is more plausible; a temporal sequence cannot be established with the onset of the AE and administration of the investigational product; or, a causal relationship is considered biologically implausible.

Possibly Related: There is a clinically plausible time sequence between onset of the AE and administration of the investigational product, but the AE could also be attributed to concurrent or underlying disease, or the use of other drugs or procedures. Possibly related should be used when the investigational product is one of several biologically plausible AE causes.

Definitely Related: The AE is clearly related to use of the investigational product.

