8.3. Study Periods

The whole study period is defined as the period of time from the date of the first dose of study drug until the end of the study.

The monotherapy period (Cohorts 1 and 3 only) is defined as the period of time from the date of the first dose of ibrutinib through the day before the addition of dexamethasone, or the day before initiation of any subsequent anti-myeloma therapy, whichever occurs first.

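### SAP Table 7 omits the protocol's summary of discontinuation AEs by severity and relationship, and four ibrutinib rows do not separate events before and after dexamethasone in Cohorts 1 and 3

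*SAP*

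**What the plan says.** **Discontinuations.** The secondary objective reads "Safety (assessed by reporting of SAEs, AEs, and treatment-related discontinuations" (protocol 3.2, repeated in SAP 1.2.2). Protocol 8.3.5 adds: "Adverse events requiring permanent discontinuation of study drug will be summarized separately, both overall and by AE severity and by relationship to study drug". In SAP Table 7, TEAEs leading to treatment discontinuation receive a listing. TEAEs leading to discontinuation of ibrutinib, and of dexamethasone, are each tabulated by system organ class and preferred term.

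**Periods.** Subjects in Cohorts 1 and 3 start on ibrutinib alone and may add weekly dexamethasone after confirmed PD. For them SAP 8.9 states: "Thus the safety data (e.g. incidence of TEAEs, laboratory values) will be presented and distinguished as with and without dexamethasone". The sentence goes on to limit this to those two cohorts and to cases where it applies. The footnote to Table 7 explains: "Study Periods refer to Whole Study Period and Monotherapy Period". SAP 8.3 defines the Monotherapy Period as running "from the date of the first dose of ibrutinib through the day before the addition of dexamethasone", or to the day before subsequent therapy if that is earlier.

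All-cause TEAEs and Grade 3 or worse TEAEs are specified as "SOC+ PT+Study Period; PT+ toxicity grade+Study Period". Related TEAEs, Grade 3 or worse related TEAEs, related serious TEAEs and TEAEs leading to discontinuation, for ibrutinib and for dexamethasone, are specified as "SOC+ PT (Whole Study Period only".

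**The concern.** The first issue is a protocol-specified output that the SAP leaves out. Which drug was stopped is not the same as whether the event was judged related to it, so the two discontinuation tables do not answer an objective framed as treatment-related discontinuations. The SAP introduction says that changes to the protocol's analysis plan are documented in the SAP, yet Section 10 lists only the two added time-to-response endpoints and the revised major hemorrhage definition.

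The second issue is narrower. The primary objective covers ibrutinib both alone and with dexamethasone. In Cohorts 1 and 3, the tables of events attributed to ibrutinib do not separate the two situations for subjects who add dexamethasone. Protocol 9.2.4 makes this matter: "Possibly related should be used when the investigational product is one of several biologically plausible AE causes". SAP 8.9.1 counts possibly related events as drug-related. An event after the addition that dexamethasone may have caused can therefore enter the ibrutinib-related rate of a monotherapy cohort. SAP 8.9.1 also keeps the highest grade and/or strongest causal relationship among repeat episodes, so a recurrence after dexamethasone can replace a milder or unrelated record from the monotherapy period.

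**Working it through.** No sample size, power or alpha is involved. The check is a comparison of texts and a count of rows.

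**1. Discontinuation AEs: required against specified**

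| Element | Protocol 8.3.5 / objective 3.2 | SAP Table 7 |
|---|---|---|
| Overall | required | listing, plus class and term tables by drug stopped |
| By severity | required | not in any discontinuation row |
| By relationship | required, and named in the objective | not in any discontinuation row |
| Recorded as a change in SAP 10 | expected from the SAP introduction | not recorded |

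This gap applies to all four cohorts.

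**2. The 21 adverse-event rows of Table 7, by summary period**

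- By Study Period: overall summary, TEAEs, Grade 3 or worse TEAEs, ibrutinib and dexamethasone dose reductions (2), ibrutinib and dexamethasone doses withheld (2), serious TEAEs, bleeding, major hemorrhage. Total 10.
- Whole Study Period only: the four ibrutinib rows and the four matching dexamethasone rows. Total 8.
- Listing only: treatment discontinuation, dose reduced or withheld, atrial fibrillation and flutter. Total 3.

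Check: 10 + 8 + 3 = 21. Of the 21 − 3 = 18 tabulated rows, 10 show the Monotherapy Period. Of the 8 that do not, the 4 dexamethasone rows need no such column, because no dexamethasone is given in that period. That leaves 4 ibrutinib rows where the split would be informative and is absent.

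**3. Direction of the effect**

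The monotherapy treatment-emergent window in SAP 5.7 lies inside the overall treatment-emergent period. A subject with a related event in the former is also counted in the latter, so the whole-study incidence cannot be lower than the monotherapy incidence. Read as a single-agent rate, it can only be equal or too high.

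**4. Size of the effect**

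Let p be the monotherapy incidence of related events, f the share of subjects who add dexamethasone, and q the share of event-free adders who then have a first related event. Then

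whole-study incidence = p + (1 − p) × f × q.

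The documents give none of p, f or q. With assumed ranges of p = 10% to 20%, f = 25% to 75% and q = 10% to 30%, the excess (1 − p) × f × q runs from 0.80 × 0.25 × 0.10 = 0.02 to 0.90 × 0.75 × 0.30 = 0.20. A spread of about 2 to 20 points from assumed inputs is not an estimate. It shows that the documents do not fix the size. Ibrutinib also continues after the addition, so part of any excess would come from longer ibrutinib exposure.

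**The case against.** **Single-agent toxicity is mostly reported separately.** A reader might infer that the plan mixes single-agent toxicity in Cohorts 1 and 3 with later toxicity in general. Table 7 does not support that. All-cause, Grade 3 or worse and serious TEAEs, dose changes, bleeding and most laboratory outputs have a Monotherapy Period summary. The secondary safety endpoint as worded (incidences and types of AEs, laboratory variables, vital signs) is available for that period. This stands and limits the point to the four rows.

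**The commitment in SAP 8.9 is qualified.** It gives examples, both of which Table 7 delivers by period, and applies only where applicable. Protocol 8.1 asks for a with/without split of efficacy endpoints only, and protocol 8.3.5 asks for none. So the period split is not a protocol requirement. The qualifier does not explain the pattern, however: the dexamethasone dose-reduction and dose-withheld rows are split, although their monotherapy column should be essentially empty, while the informative ibrutinib-related rows are not.

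**Some counts may appear elsewhere.** The overall summary is by Study Period and its contents are undefined, so it may include related events or discontinuations. Disposition tables give reasons for stopping treatment, and SAP 8.9.1 says in general terms that AEs are summarised by toxicity grade. It would therefore be too strong to say that the study will produce no such rates; the plan specifies none. The general sentence weakens the severity part of the discontinuation gap, but it does not supply the summary by relationship.

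**Decisions do not depend on it.** Expansion and success rules use CBR only, and no inferential comparison among cohorts is planned. This stands.

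**Conclusion.** Two defects hold. The firmer one is that Table 7 leaves out, for all cohorts, the summary of discontinuation AEs by severity and relationship that protocol 8.3.5 specifies and the secondary objective needs, with no entry in SAP Section 10. The second is that 4 of the 18 tabulated AE rows combine events before and after dexamethasone for those subjects in Cohorts 1 and 3 who add it, which sits poorly with the text of SAP 8.9.

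Two stronger readings are not supported. One is that all 31 subjects enrolled to these cohorts in Stage 1 (13 + 18, protocol 2.4.5) are affected: only subjects who add dexamethasone contribute mixed time, and the documents do not say how many did. The other is a stated number of points by which single-agent toxicity is overstated: the inputs are not in the documents, and later events need not be due to dexamethasone. Only the direction is established. The primary endpoint is unaffected. The change is worth making because it restores a protocol-specified output and costs little.

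**What to change.** - Add to Table 7 a summary of TEAEs leading to discontinuation of ibrutinib or of dexamethasone, by relationship and by toxicity grade, for all cohorts.
- Change the four ibrutinib rows (related TEAEs, Grade 3 or worse related TEAEs, related serious TEAEs, TEAEs leading to ibrutinib discontinuation) to system organ class and preferred term by Study Period. The four dexamethasone rows can stay as they are.
- State the assignment rule. An event belongs to the Monotherapy Period if its onset falls within the SAP 5.7 monotherapy window. A related event that starts on or after the first dexamethasone dose counts only in the Whole Study Period. The rule is needed because the third TEAE criterion in SAP 8.9.1 admits related events whatever their start date, while the SAP 5.7 window is bounded by dates.

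The cost is a SAP edit, one short date rule and some programming. Severity, relationship and action taken are already recorded for each AE (protocol 9.3.2), and the period definitions exist. Nothing in trial conduct changes. If the sponsor prefers to keep either item as it is, SAP Section 10 should record the departure from protocol 8.3.5, and SAP 8.9 should say which safety tables are not split.
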